1.2 SCHEMA

1.3 SCHEDULE OF ACTIVITIES (SOA)

Procedures	Screen Visit	Baseline ^d Visit	Study Visit 2 ^f	Study Visit 3 ^g	Study Visit 4 ^f	Study Visit 5 ^g	Final Study Visit ^f	Safety Follow Up Phone Call
	Day -3 to -1	Visit 1, Day 1	Day 4 +/- 1 day	Day 7 +/- 1 day	Day 10 +/- 1 day	Day 14 +/- 1 day	Day 21 +/- 1 day	Day 45 +/- 1 day
Informed consent	X							
Demographics	X							
Medical history	X							
Inclusion/Exclusion Criteria Evaluation	X	X						
Rapid Antigen Test for Covid-19	X ^c							
RT-PCR sample for quantitative viral load analysis		X ^c		X		X		
Serum Collection (Blood sample for immune monitoring)		X		X		X		
Physical exam	X			X		X		
Vital signs	X	X		X		X		
Pulse Oximetry	X							
Walking Oximetry	X							
Height	X							
Weight	X							
Hematology	X		X ^e	X	X ^e	X		
Serum chemistry ^a	X		X ^e	X	X ^e	X		
Pregnancy test ^b	X							
Randomization		X						
Administer study intervention		X.....X						
Concomitant medication review	X	X	X	X	X	X	X	
Adverse event review/evaluation	X	X	X	X	X	X	X	X
Patient Reported Outcomes (Modified FLU-PRO Plus)*	X*	X.....X						
Complete Case Report Forms (CRFs)	X	X	X	X	X	X	X	

a: Albumin, alkaline phosphatase, total bilirubin, direct bilirubin, bicarbonate, BUN, calcium, chloride, creatinine, glucose, LDH, phosphorus, potassium, total protein, AST, ALT, sodium, CBC/diff, LDH, , CRP, prothrombin time, activated partial prothrombin time, , D-dimer b: Serum pregnancy test (women of childbearing potential).

c: Covid-19 Confirmatory test in addition to quantitative viral load

d: Screening and Baseline can be combined

e: If clinically indicated at the discretion of the investigator

f: Visits at Day 4 (visit 2), Day 10 (visit 4), and Day 21 (final visit) will be telehealth and can be changed to in-person at the discretion of the investigator g: In the event of a complete lockdown due to Covid, visits at Day 7(Visit 3) and Day 14 (Visit 5) could be replaced by home health visit for sample collection and telehealth visit for clinical evaluation.

*Administered everyday

+ Modified FLU-PRO Plus at Screen will be completed on site to determine if patient meets inclusion criterion

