4 STUDY DESIGN

4.1 OVERALL DESIGN

This clinical research trial aims to demonstrate the safety of TQ Formula , as well as preliminary efficacy in treatment of Covid-19. The hypothesis is that treatment with TQ Formula will significantly reduce median time to sustained clinical response, defined as a reduction of scores to ≤ 2 on all symptoms of the Modified FLU-PRO Plus, compared with placebo. In addition, it is hypothesized that treatment with TQ formula will significantly reduce viral load and symptom burden from baseline to Day-7 compared to treatment with placebo.

This is a randomized, double-blind, placebo-controlled phase II study to assess the safety and efficacy of TQ Formula versus placebo in the treatment of Covid-19 in an outpatient setting. Participants will be randomized 1:1 to receive either 3 g per day of TQ Formula or placebo (identical in appearance). The participants will receive up to 14 days of dosing.

Screening Visit

The following evaluations should be completed at the Screening visit:

Informed Consent

The purpose and procedures of the study will be fully explained to potential participants. Those wishing to enroll in the study will sign a written informed consent prior to initiating any study related evaluations or procedures.

Demographics

Participant demographics, including age, race and gender will be captured and documented in the source and the electronic case report form (eCRF).

Medical History

Participant medical history, including any surgical procedures, will be captured and documented in the source and the electronic case report form (eCRF).

Inclusion/Exclusion Criteria Evaluation

Participants will be assessed to ensure that they meet all inclusion criteria and do not meet any of the exclusion criteria as listed in sections 5.1 and 5.2

Covid-19 Rapid Test (Antigen)

Participants will be given a CLIA waived rapid antigen Covid-19 test (per site standard procedures) in order to obtain same days results to use for randomization of participants. The test may be performed prior to informed consent as part of standard of care at the clinic.

Concomitant Medication Review

All concomitant medications, including vitamins and supplements, currently being taken by participants will be documented in source and in the eCRF.

Physical Exam

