5 STUDY POPULATION

5.1 INCLUSION CRITERIA

In order to be eligible to participate in this study, an individual must meet all of the following criteria:

1. Provision of signed and dated informed consent form
2. Stated willingness to comply with all study procedures and availability for the duration of the study
3. Male or female, aged 18 and over, presenting with recent mild to moderate clinical symptoms of Covid-19 infection (per FDA guidance – see appendix 3)
4. Positive COVID-19 infection confirmed with a rapid antigen test at screening and confirmed with a RT-PCR test at baseline
5. A score of ≥ 3 on a minimum of 2 symptoms on the Modified FLU-PRO Plus
6. Ability to take oral medication and be willing to adhere to the dosing regimen (Twice a day – BID for 14 days)
7. For females of reproductive potential: negative pregnancy test at screening and use of highly effective contraception method during study participation and for an additional 4 weeks after the end of study drug administration
8. For males of reproductive potential: use of condoms or other methods to ensure effective contraception with partner during study participation
9. Agreement to adhere to Lifestyle Considerations (see section 5.3) throughout study duration

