7 STUDY INTERVENTION DISCONTINUATION AND PARTICIPANT DISCONTINUATION/WITHDRAWAL

7.1 DISCONTINUATION OF STUDY INTERVENTION

Discontinuation of investigational product does not mean discontinuation from the study, and remaining study procedures should be completed as indicated by the study protocol. If a clinically significant finding is identified (including, but not limited to changes from baseline) after enrollment, the investigator or qualified designee will determine if any change in participant management is needed. Any new clinically relevant finding will be reported as an adverse event (AE).

The data to be collected at the time of study intervention discontinuation will include the following:

- Reason for discontinuation
- Adverse events
- Changes to concomitant medications

If a participant discontinues investigational product, all study visits will continue as per the Schedule of Assessments (SOA).

Participants who are randomized but who subsequently have a negative RT-PCR Covid-19 test, will discontinue investigational product, but will continue to be followed up for safety and efficacy.

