8.1 EFFICACY ASSESSMENTS

Covid-19 Quantitative Viral Load (RT-PCR)

Participants will have an RT-PCR sample taken at baseline, day 7 and day 14 to measure quantitative viral load and viral load clearance. These samples will be sent to a central laboratory for analysis.

Patient Reported Outcomes

Participants will receive the Modified FLU-PRO Plus questionnaire (Appendix 2) to complete on a daily basis for the duration of the study, from randomization to final study visit. The responses will be used to measure severity and change in Covid-19 symptoms from baseline.

Serum Collection (Blood sample for immune monitoring)

Participants will have blood collected for immune monitoring. This testing will explore pharmacokinetics and inflammatory cytokines, coagulation factors and effector immune cells in samples. These samples will be sent to a central laboratory for analysis.

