## 3.3 Inclusion/Exclusion Criteria

### 3.3.1 Inclusion Criteria

In order to be eligible to participate in this study, an individual must meet all of the following criteria:

1. Provision of signed and dated informed consent form
2. Stated willingness to comply with all study procedures and availability for the duration of the study
3. Male or female, aged 18 and over, presenting with recent mild to moderate clinical symptoms of Covid-19 infection (per FDA guidance – see appendix 3)
4. Positive COVID-19 infection confirmed with a rapid antigen test at screening (or RT-PCR within the last 3 days) and confirmed with a RT-PCR test at baseline
5. A score of  $\geq 3$  on a minimum of 2 symptoms on the Modified FLU-PRO Plus
6. Ability to take oral medication and be willing to adhere to the dosing regimen (Twice a day – BID for 14 days)
7. For females of reproductive potential: negative pregnancy test at screening and use of highly effective contraception method during study participation and for an additional 4 weeks after the end of study drug administration
8. For males of reproductive potential: use of condoms or other methods to ensure effective contraception with partner during study participation
9. Agreement to adhere to Lifestyle Considerations (see section 5.3) throughout study duration

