#### 4.1.2 Secondary Efficacy Endpoints

1. Measurement of change in quantitative viral load from baseline, Day 7, and Day 14 using RT-PCR in participants taking 3 g TQ Formula (500 mg per capsule, 3 capsules BID) versus participants taking placebo with COVID-19 infection.
2. Percentage of negative/undetectable RT-PCR (i.e., viral clearance) on Day-7 and Day-14 in participants taking 3 g TQ Formula (500 mg per capsule, 3 capsules BID) versus participants taking placebo
3. Measurement of severity of, and change in, Covid-19 symptoms per total score as well as sub-scores (Nose, Throat, Eyes, Chest/Respiratory, Gastrointestinal, Body/Systemic, Taste/Smell) measured through Modified FLU-PRO Plus from Day 1 through Day 14 in participants with COVID-19 infection treated either with 3 g TQ Formula (500 mg per capsule, 3 capsules BID) or placebo.
4. Correlation Coefficient of quantitative viral load and symptom severity at baseline, at Day 7, and Day 14 in participants taking 3 g TQ Formula (500 mg per capsule, 3 capsules BID) versus participants taking placebo

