Secondary estimand-2 is defined to be the proportion difference of patients with RT-PCR negative/undetectable viral loads between participants taking 3 g TQ Formula (500 mg per capsule, 3 capsules BID) and participants taking placebo regardless of whether or not they actually receive their assigned therapy (ITT) and assuming that their hospitalization and treatment discontinuation rates will be similar. To address this estimand, the percentages of RT-PCR negative/undetectable viral loads between the two study arms will be estimated and compared using Fisher's Exact test at Day-7 and Day-14 visits. The above mentioned intercurrent events for

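### Aim-2 counts any negative RT-PCR at Day 7 or Day 14 as viral clearance, without requiring detectable virus at baseline

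*SAP*

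**What the plan says.** SAP 4.1.2 defines the second secondary endpoint as "Percentage of negative/undetectable RT-PCR (i.e., viral clearance) on Day-7 and Day-14". SAP 5.3.3, Aim-2, makes the estimand the between-arm difference in the proportion negative or undetectable, on an intention-to-treat basis. It adds that "the percentages of RT-PCR negative/undetectable viral loads between the two study arms will be estimated and compared using" Fisher's exact test at each of the two visits. SAP 5.2 defines the ITT set as everyone randomised, including people never dosed and people with protocol violations. The supplementary logistic models for Aim-2 name gender and age as factors, not baseline RT-PCR status.

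On entry, Protocol 5.1 criterion 4 wants infection "confirmed with a rapid antigen test at screening and confirmed with a RT-PCR test at baseline". SAP 3.3.1 widens the screening test ("or RT-PCR within the last 3 days) and confirmed with a RT-PCR test at baseline"). In the Protocol 1.3 schedule, the baseline sample carries the footnote "Covid-19 Confirmatory test in addition to quantitative viral load".

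The operational text allows randomisation before the baseline RT-PCR is known. Protocol 4.1 has the antigen test done "in order to obtain same days results to use for randomization of participants". Protocol 8.1 says that RT-PCR samples measure viral load and "viral load clearance. These samples will be sent to a central laboratory for analysis". Protocol 7.1 foresees the result: "Participants who are randomized but who subsequently have a negative RT-PCR Covid-19 test" stop product but stay in follow-up for efficacy as well as safety.

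**The concern.** Clearance means that virus was present and then was not. A participant whose baseline RT-PCR is negative has no virus to clear on that assay. If the Day 7 or Day 14 sample is negative too, the plan still adds one to both the numerator and the denominator of that arm's clearance percentage.

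Two things follow. The reported percentage mixes clearance with absence of detectable virus from the start, so it cannot be read as a clearance rate. And participants whose result says nothing about antiviral effect dilute the difference between arms. With about 26 per arm, one participant moves an arm's percentage by nearly 4 points (1/26 = 3.8%), so one or two such people are visible in the result. Deciding how to treat them after unblinding would be a post-hoc choice.

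**Working it through.** The documents state no rate, power or sample size for Aim-2, so there is no figure to reproduce. What follows is the route into the analysis and then an illustration.

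**Route.** Eligibility needs a positive baseline RT-PCR, but randomisation proceeds on the antigen result while the RT-PCR is at the central laboratory. A negative that comes back later belongs to a randomised participant. ITT keeps that person, Protocol 7.1 keeps them in efficacy follow-up, and Aim-2 sets no baseline condition. Protocol 7.1 does not name the visit; baseline is the natural reading. The SAP cites Protocol Version 6.0, where 7.1 may read differently, but the gap is in the SAP's own definition.

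**Inputs.** From the documents: 26 per arm (up to 30) and about 20% attrition (SAP 3.2); two-sided 0.05 (Protocol 9.4.1). Assumed: baseline-negative share f = 2%, 5%, 10%, equal in both arms; share s of those negative again at the visit, equal in both arms; illustrative clearance rates among participants detectable at baseline.

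**Formulas.** Expected baseline negatives per arm = 26f. Chance of at least one among 52 = 1-(1-f)^52. Reported rate = p(1-f) + s·f. Reported difference = (p1-p0)(1-f), because s·f cancels.

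| | f = 0 | 2% | 5% | 10% |
|---|---|---|---|---|
| Baseline negatives per arm | 0 | 0.5 | 1.3 | 2.6 |
| Chance of at least one in 52 | 0 | 65% | 93% | 99.6% |
| True 40% reported as, s = 1 | 40% | 41.2% | 43.0% | 46.0% |
| True 40% reported as, s = 0.5 | 40% | 40.2% | 40.5% | 41.0% |
| True 20-point difference reported as | 20 | 19.6 | 19.0 | 18.0 |
| Fisher power, 30% vs 65%, 26 per arm, s = 1 | 62.3% | 60.0% | 56.7% | 51.9% |
| Same, 21 per arm (26 × 0.8 = 20.8) | 49.2% | 47.2% | 44.3% | 39.7% |
| Fisher power, 40% vs 60%, 26 per arm, s = 1 | 20.8% | 20.0% | 19.0% | 17.6% |
| Fisher type I error, 40% vs 40%, 26 per arm, s = 1 | 2.8% | 2.8% | 2.7% | 2.6% |

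Power and type I error are exact, by enumeration. Type I error stays below 5% throughout.

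**What restriction recovers.** Exact Fisher power in the baseline-detectable set (arm sizes binomial with mean 26(1-f)), 30% vs 65%, is 64.8%, 65.8% and 63.1%. These exceed the 62.3% with nobody lost, which cannot be a real gain. They arise because Fisher's test is discrete: its size at 40% vs 40% is 3.4-3.6% in that set against 2.6-2.8% in the diluted one. A smooth pooled-variance approximation removes this:

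power = Φ{[Δ - 1.96·√(2p̄(1-p̄)/n)] / √([p0(1-p0)+p1(1-p1)]/n)}

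At n = 26, undiluted: [0.35 - 1.96 × 0.1385] / 0.1297 = 0.605, so power is 72.8%. Diluted, at f = 2%, 5%, 10%: 70.8%, 67.9%, 63.0%. Restricted, with n = 26(1-f): 71.8%, 70.4%, 68.0%. The gain is about 1, 2.6 and 5 points. It also depends on n and on the rates: for 30% vs 70% at 30 per arm, exact Fisher gives 79.3% diluted against 79.0% restricted (28 per arm) at f = 5%, and 74.3% against 76.3% (27 per arm) at 10%.

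**The case against.** The case for leaving the plan alone has several parts.

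- **Eligibility already requires a positive baseline RT-PCR.** True, so the intended population is baseline-positive. But eligibility does not define the analysis set, and ITT expressly keeps violators.
- **The estimand is explicit and computable; clearance is only a gloss.** This stands in part. The difference in proportion negative among all randomised is a legitimate randomised comparison. The gloss is nevertheless how the result will be read.
- **The per-protocol version deals with it.** It might, but the SAP does not say that a negative baseline RT-PCR excludes anyone. That set also conditions on compliance and completed visits after randomisation, so it does not isolate this issue.
- **The count of baseline negatives will be visible anyway.** Largely so: SAP 5.1 summarises baseline variables, SAP 7.9 lists tables of rapid-test and RT-PCR results, and Protocol 9.4.8 presents baseline measures by arm. No new table is needed, only the count beside the Aim-2 result.
- **The size rests on an undocumented f.** This stands in full. If f is near zero, the effect is negligible.

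A reader might infer three stronger things. The first is bias in favour of one arm. With 3 baseline negatives against 0 at 30 per arm and no effect at 40%, expected rates are (3 + 27 × 0.4)/30 = 46% and 40%; but such an imbalance is chance under randomisation, and the test's type I error covers it. The second is that Protocol 7.1 contradicts criterion 4. It does not: one sets entry, the other says what follows a negative result after randomisation, and only the visit is unnamed. The third is that the Aim-1 slope model has the same fault. Nothing computed here shows that, and the SAP deliberately uses all available data there.

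**Conclusion.** The concern holds as a definitional gap. A participant RT-PCR-negative at baseline and again at Day 7 or Day 14 is counted as cleared, so the reported percentage is not a clearance rate. The (1-f) shrinkage requires the baseline-negative share, and the chance that those participants stay negative, to be equal in both arms. On an assumed f of 2-10% the loss is 0.4 to 2 points of a true 20-point difference, and 2 to 10 points of exact Fisher power for 30% vs 65% at 26 per arm.

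Confidence is high that the definition lacks a baseline condition. It is low on how many participants are affected, because the documents give no rate. Nor should the exact Fisher contrast be read as the benefit of the change: on the smooth approximation, restriction recovers only about 1 to 5 points at 26 per arm. Protocol 9.4.1 treats secondary results as hypothesis-generating. The case for change rests mainly on giving the endpoint its proper meaning before unblinding, less on power.

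**What to change.** In SAP 4.1.2 and 5.3.3 Aim-2, define viral clearance as RT-PCR detectable at baseline and negative or undetectable at the visit. Analyse it in randomised participants with a detectable baseline sample, and keep the all-randomised comparison of proportions negative alongside. State the number of baseline negatives by arm with the result; the tables already planned should largely supply it.

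The cost is one endpoint sentence, one analysis-set definition and one reported count. The baseline sample is already collected and precedes treatment, so the restricted comparison remains randomised. The downside is a few participants lost from the clearance analysis, about 0.5 to 2.6 per arm on the assumed range.

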# BOSS-Covid-19 Study (BOSS-001)

the primary endpoint are applicable for Secondary estimand-1 as well. Therefore, hospitalization-free, while-on-study and per-protocol treatment versions of the above estimand will also be considered within each population definitions above. Beyond the single test of independence at each time point, Logistic Regression models will also be constructed to investigate the interaction of the study arms with other factors of interest such as gender, age, etc.

## Analysis plan for Secondary Aim-3:

Secondary estimand-3 is defined to be the difference of total and subdomain symptom scores measured through Modified FLU-PRO Plus questionnaire between participants taking 3 g TQ Formula (500 mg per capsule, 3 capsules BID) and participants taking placebo regardless of whether or not they actually receive their assigned therapy (ITT) and assuming that their hospitalization and treatment discontinuation rates will be similar. To address this estimand, the differential change of total and subdomain symptom severity score measured by Modified FLUPRO Plus overtime between the two-study arm will be estimated and compared between the two study arms. As the total and subdomain symptom severity score will be measured at Baseline (Day-1) and on each day through Day-14, the outcome variables of interest will be a longitudinal interval-scale measures. To assess the differential behaviour of total and subdomain symptom scores overtime between the two study arms, Random Coefficients Models will be utilized where total and each of the subdomain symptom severity score will be the dependent variables and study arm and time will be main predictors. Total and subdomain symptom severity scores may be subjected to some data transformation (e.g., log transformation) to improve the model fit and assumptions as necessitated by model diagnostics. In addressing this objective, all available data will be utilized; that is, in addition to the evaluable patients, data from non-evaluable patients such as data only at baseline visit or data just at baseline and Day-10 for example will be used to improve the local fit of the underlying model. To assess differential behavior in total symptom severity score, time\*study-arm interaction will be investigated as well. When scientifically indicated, aggregated symptom severity scores may be defined through combining a set of subdomains such as Nose, Eyes, And Throat. The above mentioned intercurrent events are applicable for Secondary estimand-1 as well. Therefore, hospitalization-free, while-on-study and per-protocol treatment versions of the above estimand will also be considered within each population definitions above. For the above analyses, the MIXED procedure of SAS software will be utilized.

# BOSS-Covid-19 Study (BOSS-001)

## Analysis plan for Secondary Aim-4:

Secondary estimand-4 is defined to be the assessment of whether or not a significant correlation between quantitative viral load and symptom severity exists and if so, whether or not such a linear association is dependent on the study arm. To address this estimand, the association between quantitative viral load and symptom severity will be investigated through linear regression models using the GLM procedure of SAS software, where total symptom severity score will be the dependent variable predicted by the quantitative viral load measures in the model at each visit. Study-Arm\*viral load interaction will be added to the model to investigate if any association between viral load and symptom severity is mitigated by the study treatment. The above mentioned intercurrent events are applicable for Secondary estimand-1 as well. Therefore, hospitalization-free, while-on-study and per-protocol treatment versions of the above estimand will also be considered within each population definitions above.

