9.1 STATISTICAL HYPOTHESES

The primary statistical hypotheses are:

1. Treatment with 3 g TQ Formula (500 mg per capsule, 3 capsules BID) given orally on outpatient basis (study drug) will significantly reduce median time to sustained clinical response compared to placebo in participants with COVID-19 infection treated in the outpatient setting. Sustained clinical response is defined as a reduction of scores to ≤ 2 on all symptoms of the Modified FLU-PRO Plus.

The secondary statistical hypotheses are as follows:

1. Study drug will significantly reduce quantitative viral load by Day-14 compared to placebo in participants with COVID-19 infection treated in the outpatient setting.
2. Study drug will significantly increase the percentage of negative/undetectable RT-PCR viral load at Day 7 and Day 14 in participants taking 3 g TQ Formula (500 mg per capsule, 3 capsules BID) versus participants taking placebo in participants with COVID-19 infection
3. Study drug will significantly reduce duration and severity of symptoms overall and within each symptom domain overtime from Day 1 to Day 14 compared to placebo in participants with COVID-19 infection
4. There is a significantly positive correlation between quantitative viral load and symptom severity at baseline, at Day 7, and Day 14 in patients with COVID-19 infection

5. Study drug will lead to acceptable AE and SAE profiles compared to placebo

- Primary Efficacy Endpoint(s):
 1. Measurement of the difference in median time to sustained clinical response in participants taking 3 g TQ Formula (500 mg per capsule, 3 capsules BID) versus participants taking placebo.
- Secondary Efficacy Endpoint(s):
 1. Measurement of change in quantitative viral load from baseline, Day 7, and Day 14 using RTPCR in participants taking 3 g TQ Formula (500 mg per capsule, 3 capsules BID) versus participants taking placebo with COVID-19 infection.
 2. Percentage of negative/undetectable RT-PCR (i.e., viral clearance) on Day-7 and Day-14 in participants taking 3 g TQ Formula (500 mg per capsule, 3 capsules BID) versus participants taking placebo
 3. Measurement of severity of and change in Covid-19 symptoms per total score as well as sub-scores (Nose, Throat, Eyes, Chest/Respiratory, Gastrointestinal, Body/Systemic, Taste/Smell) measured through Modified FLU-PRO Plus from Day 1 through Day 14 in participants with COVID-19 infection treated either with 3 g TQ Formula (500 mg per capsule, 3 capsules BID) or placebo

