The third secondary endpoint of this clinical trial is the differential change of total and subdomain symptom severity score measured by Modified FLU-PRO Plus overtime between the two-study arm. As the total and subdomain symptom severity score will be measured at Baseline (Day-1) and on each day through Day-14, the outcome variables of interest will be a longitudinal interval-scale measures. To assess the differential behaviour of total and subdomain symptom scores overtime between the two study arms, Random Coefficients Models will be utilized where total and each of the subdomain symptom severity score will be the dependent variables and study arm and time will be main predictors. Total and subdomain symptom severity scores may be subjected to some data transformation (e.g., log transformation) to improve the model fit and assumptions as necessitated by model diagnostics. In addressing this objective, all available data will be utilized; that is, in addition to the evaluable patients, data from non-evaluable patients such as data only at baseline visit or data just at baseline and Day-10 for example will be used to improve the local fit of the underlying model. To assess differential behavior in total symptom severity score, time*study-arm interaction will be investigated as well. When scientifically indicated, aggregated symptom severity scores may be defined through combining a set of subdomains such as Nose, Eyes, And Throat.

Association between quantitative viral load and symptom severity will be investigated through regression models, where total symptom severity score will be the dependent variable predicted by the quantitative viral load measures in the model at each visit. Study-Arm*viral load interaction will be added to the model to investigate if any association between viral load and symptom severity is mitigated by the study treatment.

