## 3.7 Secondary Objective

1. To compare the viral load profile over time (from baseline through to Day 14) between treatment with 3 g TQ Formula (500 mg per capsule, 3 capsules BID) given orally on outpatient basis and placebo in participants with COVID-19 infection treated in the outpatient setting
2. To compare the percentage of RT-PCR negative/undetectable (i.e., viral clearance) on Day 7 and Day 14 in participants taking 3 g TQ Formula (500 mg per capsule, 3 capsules BID) versus participants taking placebo
3. To compare the duration and severity of symptoms (measured by Modified FLU-PRO Plus) over time from Day 1 through Day 14 in total FLU-PRO Plus symptom severity score overall and in sub-domain scores (namely, Nose, Throat, Eyes, Chest/Respiratory, Gastrointestinal, Body/Systemic, Taste/Smell), between treatment with 3 g TQ Formula (500 mg per capsule, 3 capsules BID) given orally on outpatient basis and placebo in participants with COVID-19 infection
4. To investigate if there exists an association between viral load and symptom severity by study arm and if such associations change overtime.

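### Secondary objective 4 asks whether the viral load-symptom association changes over time, but no planned analysis tests that change

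*SAP*

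**What the plan says.** The objective (SAP 3.7; the same in Protocol 1.1 and 3) reads: "To investigate if there exists an association between viral load and symptom severity by study arm and if such associations change overtime". It has two parts, dependence on arm and change over time.

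The endpoint (SAP 4.1.2) is the "Correlation Coefficient of quantitative viral load and symptom severity at baseline, at Day 7, and Day 14". The hypothesis (Protocol 9.1) is also visit by visit: "There is a significantly positive correlation between quantitative viral load and symptom severity at baseline, at Day 7, and Day 14".

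In SAP 5.3.3, estimand-4 asks whether a correlation exists and, if so, "whether or not such a linear association is dependent on the study arm". Time is not mentioned. The method is a linear regression in PROC GLM, set up as follows: "where total symptom severity score will be the dependent variable predicted by the quantitative viral load measures in the model at each visit". Protocol 9.4.3 describes the same regression. The one interaction named is study arm by viral load: "viral load interaction will be added to the model to investigate if any association between viral load and symptom severity is mitigated".

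Protocol 9.4.1 sets a two-sided 0.05 level, applies no multiplicity correction to secondary tests, and treats their results as hypothesis-generating.

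**The concern.** Followed as written, Aim-4 gives three regressions and no comparison between them. There is no viral load by visit term, no contrast of slopes or correlations between visits, and no within-participant covariance that such a contrast would need. Half of a stated objective has no analysis.

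This looks like an omission and not a choice. Aims 1 and 3 use random coefficients models with time as a predictor, and the exploratory aims in SAP 5.3.4 do the same. Those models cannot fill the gap, because each follows one outcome over time and not the association between two.

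Two things are at stake. The method for the missing half would have to be chosen after the data are seen. And the visit-by-visit hypothesis invites an informal answer, namely that the association was present at one visit and absent at another, which is not evidence of change.

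**Working it through.** The documents give no power or precision figure for Aim-4, so there is none to reproduce.

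**1. Question against analysis**

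| Place | Association exists | Depends on arm | Changes over time |
|---|---|---|---|
| Objective 4 (SAP 3.7) | yes | yes | yes |
| Hypothesis 4 (Protocol 9.1) | at each visit | no | no |
| Estimand-4 (SAP 5.3.3) | yes | yes | no |
| Model (SAP 5.3.3, Protocol 9.4.3) | at each visit | arm x viral load | no term |

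The wording could also mean one GLM on stacked visits. That model still has no viral load x visit term. If the term were added with visits treated as independent, its test would be mis-sized: simulated type I error was 1.7% against a nominal 5% (52 patients, correlation 0.3 at each visit, within-person correlation 0.5).

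**2. What comparing per-visit significance would do**

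Inputs from the documents: three visits with viral load (SAP 3.1), two-sided 0.05 (Protocol 9.4.1), 52 to 60 patients (SAP 3.2), and 40 if only the 20 per arm of the power statement are counted. Assumed, because the documents give no values: a true correlation r that is the same at every visit, within-person correlation c between visits of 0 to 0.7, and complete data.

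For one visit, the Fisher z statistic has mean atanh(r) x sqrt(n - 3), which gives power p. For three independent tests, the chance of a mixed result (at least one significant, at least one not) is 1 - p^3 - (1 - p)^3.

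Example with n = 52 and r = 0.30: 0.3095 x 7 = 2.167; p = Phi(2.167 - 1.96) = 0.582; mixed = 1 - 0.197 - 0.073 = 0.73.

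| True r, constant | Independent tests, n = 52 (formula) | n = 52, c = 0.5 (simulated) | n = 60, c = 0.5 | n = 40, c = 0.5 | One arm, n = 26, c = 0.5 |
|---|---|---|---|---|---|
| 0 | 14% | 14% | 14% | - | 15% |
| 0.2 | 62% | 54% | 57% | 46% | 36% |
| 0.3 | 73% | 62% | 58% | 63% | 56% |
| 0.4 | 40% | 34% | 24% | 51% | 62% |
| 0.5 | 9% | 7% | 4% | 19% | 48% |
| 0.6 | 0.6% | 0.5% | 0.1% | - | 19% |

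Over c from 0 to 0.7 with n = 52, the ranges are 44-63% at r = 0.2, 50-73% at 0.3, 29-39% at 0.4 and 6-8% at 0.5. The lowest value for r of 0.2 to 0.4 is 22% (n = 60, c = 0.7, r = 0.4). In the same simulations a joint 2-df viral load x visit test, fitted with an unstructured covariance, signalled a false change in about 4.5% to 7%. With n = 52 and c = 0.5 it had about 70% power for true correlations of 0.1, 0.3 and 0.5 across the visits.

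**3. Slope or correlation**

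With slope b, viral load SD s and residual variance v, the correlation is b x s / sqrt(b^2 x s^2 + v). Take b = 0.5 and v = 0.75. At s = 1 it is 0.50. At s = 0.5 it is 0.25 / sqrt(0.0625 + 0.75) = 0.28. The correlation can move while the slope stays fixed.

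**4. Which joint model**

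Viral load is itself time-varying. Assume 52 or 60 patients, a same-visit slope of 0.40 at every visit, residual and lag-1 viral load correlations of 0.5, and an added effect of the previous visit's viral load of 0.4 per SD. An unstructured-covariance model then pulled the baseline slope from 0.40 to about 0.22-0.26. It signalled a false change in about 8% to 21% of trials, depending on the residual variance and the correlation pattern. Working independence with participant-clustered robust standard errors left the slope at 0.40 and gave about 6% to 9%, or about 4% to 6% with a leverage-corrected sandwich. With no lagged effect, both approaches gave about 6% to 8% without that correction.

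**The case against.** The per-visit regressions are valid for what hypothesis 4 and the endpoint ask, which is an association at each visit. A reader might infer that ignoring the within-participant correlation makes them wrong. It does not; that correlation matters only once visits are compared. This part of the objection stands.

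A reader might also infer that the plan will often suggest a change that is not there. The documents do not support that. They give no expected correlation, and the mixed-result rate is low near zero and from 0.5 upward in the whole sample. The SAP nowhere tells the reader to compare significance between visits. Nor are p-values and correlations all that would be available, since a linear regression also gives a slope and standard error at each visit. That those correlations will shrink by Day 14 is likewise unproven: the documents give no viral load distribution, and partial clearance could widen the spread.

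Finally, this is the fourth secondary aim, its results are declared hypothesis-generating, and SAP 2.2 allows unplanned exploratory analyses. That lowers the weight of the point. It does not supply the missing analysis, because a test chosen later would be post hoc for a question the plan had already posed.

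**Conclusion.** The gap is real and can be read directly from the documents: objective 4 asks about change over time, estimand-4 drops it, and no term or contrast in Aim-4 can answer it. This conclusion rests on no assumption.

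The size of the risk from comparing per-visit significance is conditional. For a constant true correlation of 0.2 to 0.4, three visits disagree in roughly 25% to 75% of trials. With 52 patients the rate is about 14% at zero, 10% or less at 0.5 and about 1% at 0.6; within one arm of 26 it remains substantial at 0.5. These figures assume normal, complete data and a reader who makes that comparison. The point should be corrected, but no treatment-effect conclusion depends on it.

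**What to change.** Restore change over time to estimand-4, and say that it means change in the slope. In SAP 5.3.3 and Protocol 9.4.3, stack baseline, Day 7 and Day 14 in one model of total score on log10 viral load, visit, arm, viral load x visit and viral load x arm. The 2-df viral load x visit test answers the question of change. Add viral load x visit x arm as exploratory, because the objective speaks of associations by arm.

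Use working independence with participant-clustered robust standard errors, preferably with a small-sample correction at this sample size. Avoid relying on an unstructured-covariance mixed model, whose visit-specific slopes can be biased if earlier viral load affects later symptoms. State the value given to undetectable results before the log is taken.

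Report visit-specific slopes and their differences with 95% confidence intervals. Keep the per-visit correlations as description, with a note that they also move with the spread of viral load.

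The cost is one paragraph in each document and slightly wider intervals. The data are already collected, and the planned software can fit the model.
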